# 1. Introduction

## Background: osteoarthritis

Osteoarthritis (OA) is the most common degenerative joint disease and a leading cause of chronic pain and physical disability in older individuals. The lifetime risks of developing symptomatic knee OA are estimated at 40% in men and 47% in women (1).

The hallmark symptom of OA is pain. This is the symptom that drives individuals to seek medical attention and contributes to functional limitation and reduced quality of life (2); the alleviation of pain is the main motivation for treatment, including nonpharmacologic, pharmacologic, and surgical approaches. End-stage knee OA is successfully treated with joint replacement surgery, but effective management of mild to moderate radiographic knee OA refractory to conservative treatment can be difficult.

Although OA was viewed as a "wear-and-tear" disease for many decades, it is now generally accepted to be a low- grade inflammatory disease of synovial joints and a biomechanical wholeorgan disease (3). Angiogenesis is believed to contribute to the genesis of inflammation and particularly to its maintenance (4). The new increased vascular network provides inflammatory cells access to the synovium and other joint tissues and promotes additional hyperplasia and inflammation in other vessels, leading to bone and cartilage destruction (4). In addition, studies on OA have shown that angiogenesis may contribute to chronic pain by enabling the growth of new unmyelinated sensory nerves along their path (5).

Selective genicular artery embolization (GAE) is an innovative, minimally invasive procedure that involves catheterization of the genicular artery and partial occlusion of this vessel (embolization) with particles. Preliminary data from feasibility studies in humans have been completed and show an excellent safety profile and efficacy (6, 7). The desired effect is to decrease vascularity, leading to a reduced inflammatory response. The purpose of this investigation is to confirm the safety and efficacy of GAE in adults with knee OA.

#### Background: embolization

The concept and practice of therapeutic arterial embolization is over 50 years old. Embolization has traditionally been used to treat acute hemorrhage (e.g. embolization of the gastroduodenal artery for gastrointestinal hemorrhage). Over the past twenty years, the practice of embolization has evolved to treat patients with both benign and malignant tumors. For example, liver cancer is now routinely treated via embolization of the hepatic artery (8). Benign symptomatic uterine fibroids are typically treated with particle embolization of the uterine arteries in the pelvis (9). Uterine fibroid embolization now has level I evidence as a treatment option by the American College of Obstetricians and Gynecologists for patients with symptomatic uterine fibroids (10).

Embolization of arteries in the musculoskeletal system is typically performed in the setting of trauma in order to stop ongoing hemorrhage or for pre-operative embolization of hypervascular tumors. Treatment of bleeding arteries was quickly recognized as one potential therapeutic application of arterial embolization in the knee. Several reports of genicular artery embolization for the treatment of hemarthrosis after knee surgery have shown to result in significant symptomatic clinical improvement (11, 12).

## Rationale

The knee receives its blood supply from the genicular arteries, branches from the superficial femoral and popliteal arteries. Deliberate partial blockage of the genicular arteries (embolization) leads to reduction of the inflammatory response, with potential improvement in pain. Recently, Okuno and colleagues reported their experience with genicular artery embolization for patients with mild-to-moderate knee osteoarthritis. In their pilot study, 14 patients underwent embolization (7). No major adverse events were reported. There was a dramatic and rapid reduction in symptom and pain scores of patients.

In 2017, the same authors reported their results of genicular artery embolization performed on 95 knees in 72 patients (6). All patients had pain that was resistant to conservative treatment, such as oral nonsteroidal ant-inflammatory drugs, oral opioid agents, physical therapy, stretching, muscle strengthening, or intraarticular injection of hyaluronic acid. The distribution of local tenderness (indicating the presence of inflammation) was evaluated in all cases immediately before transcatheter arterial embolization and subdivided into eight areas to determine the key arteries to be treated. After selective catheterization of the appropriate genicular artery, imipenem/cilastatin sodium was used as the embolic material in 88 knees in 65 patients. Patients who had contraindications to imipenem/cilastatin (ie, a history of hypersensitivity or allergy to antibiotic agents or treatment with valproic acid) were treated with 75-µm Embozene microspheres instead (7 knees in seven patients).

Mean Western Ontario and McMaster Universities Osteoarthritis Index (WOMAC) pain scores decreased significantly from 12.1 at baseline to 6.2 at 1 month, 4.4 at 4 months, 3.7 at 6 months, 3.0 at 12 months, and 2.6 at 24 months after the first transcatheter arterial embolization procedure (all P < .001). The intent-to-treat clinical success rate at 6 months of follow-up was 86.3% (95% CI, 78%–92%). The mean total WOMAC score also decreased significantly from 43 at baseline to 24, 14.8, 11.2, 8.2, and 6.2 at 1, 4, 6, 12, and 24 months, respectively (all P < .001). The mean VAS score significantly decreased from 72 at baseline to 38, 29, 19, 13, and 14 at 1, 4, 6, 12, and 24 months, respectively (all P < .001). Patients reported a decrease in the dose of medication used and frequency of other treatments after the procedure.

No serious adverse events were noted. Minor complications occurred, such as moderate subcutaneous hemorrhage at the puncture site and transient cutaneous color change on the treated knee, all of which resolved without treatment.

While these single center results show a great deal of promise, the vast majority of patients underwent embolization with imipenem/cilastatin, which is not readily available in the United States. Seven patients underwent embolization with small calibrated microspheres (75- $\mu$ m Embozene, Boston Scientific). While equivalent success rates were shown between the two embolics, the low number of patients treated with Embozene microspheres precludes a true comparative analysis.

Embozene particles are FDA approved for the embolization of hypervascular tumors and arteriovenous malformations. Several studies have shown excellent safety and efficacy with regards to tumor control and objective response in liver cancer (13, 14). It has been used extensively for the treatment of symptomatic uterine fibroids, where Embozene embolization of the uterine arteries results in necrosis of uterine fibroids and cessation of abnormal vaginal bleeding (9). Other proven uses include embolization of arteriovenous malformations and fistulas (15).

Genicular artery embolization appears to be safe and effective for the treatment of knee osteoarthritis based on a single center study. Its mechanism of action in decreasing knee hypervascularity and inflammation appears consistent with other studies. Embozene particles are FDA-approved for the treatment of hypervascular tumors, and have shown promise in this arena. Based on these principles, a study of the safety and efficacy of Embozene particles for genicular artery embolization is warranted.

# 2. Study Objectives

# 2.1 Primary Objective

The primary objective of this investigation is to assess safety of genicular artery embolization (GAE) for knee osteoarthritis (OA) using Embozene particles.

#### 2.2 Secondary Objectives

The secondary objectives of this investigation are to assess efficacy using the following outcomes, compared to baseline values when appropriate:

- Improvement in pain
- Improvement in WOMAC score
- Change in radiographic imaging

# 3. Eligibility Criteria

#### 3.1 Inclusion Criteria

Subjects must meet all of the following inclusion criteria in order to be eligible for this study:

- Provided informed consent
- Age  $\geq$  40 years and less than 80 years
- Life expectancy greater than 12 months
- Ineligibility for or refusal of surgical management
- Moderate-severe knee pain as determined by visual analog scale  $\geq 4$
- Osteoarthritis based on xray. Kellgren-Lawrence score  $\geq$  1 based on radiograph completed within 6 months of procedure date.
- Local knee tenderness
- Resistant/failed conservative treatment (e.g. NSAIDS/physical therapy/steroid joint injection) for at least 3 months.

#### 3.2 Exclusion Criteria

Subjects that meet any of the following exclusion criteria will not be eligible for this study:

- Mild knee pain as determined by visual analog scale < 4
- Chronic renal insufficiency (serum creatinine >2 mg/dL)
- Uncorrectable bleeding diathesis
  - INR >1.6
  - Platelets <50,000
- Significant arterial atherosclerosis that would limit selective angiography
- Allergy to iodinated contrast agents that is not responsive to steroid management
- Active Infection or malignancy
- Appropriate candidate for knee replacement surgery determined by clinical and physical examination
- Recent (within 3 months) or active cigarette use
- Prior knee arthroplasty surgery in the subject knee
- Active pregnancy

# 4. Study Design

This is a single-center, prospective, single arm investigational study to evaluate the safety of genicular artery embolization (GAE) for treatment of symptomatic knee osteoarthritis (OA). In addition, the improvement as part of efficacy will be reported. All subjects will have either failed or be intolerant to conservative management, and be ineligible for or refuse surgical intervention. Subjects will be considered enrolled in the study once they have provided informed consent and have been determined to meet all eligibility criteria. A total of 40 subjects will be enrolled in the single treatment arm of the study and will be followed for 12 months. The subjects will be stratified according to arthritis severity based on imaging, with 20 subjects allocated to mild-moderate arthritis based on x-ray (Kellgren-Lawrence x-ray grade 1-2), and with 20 subjects allocated to severe arthritis based on x-ray (Kellgren-Lawrence x-ray grade 3-4). The stratification will not be randomized, but each category will be limited to 20 patients.

The study will involve a screening period in which patient eligibility is determined. Once eligibility is confirmed, subjects will undergo GAE with Embozene microspheres (100 micron). Following treatment, subjects will return for follow-up visits at 1 week (± 4 days), 1 month (± 2 weeks), 3 months (± 2 weeks), 6 months (± 2 weeks), and 12 months (± 2 weeks) post-procedure. At these visits, subjects will complete the Western Ontario and McMaster Universities Osteoarthritis Index (WOMAC) score, and a visual analog scale (VAS) score, undergo a directed physical examination, and report any new adverse events (AEs). At 3 months of follow-up, subjects will also undergo knee x-ray. At the 12 month follow-up, subjects will also complete a patient-reported outcomes (PRO) and patient global impression of change (PGIC) questionnaire.

The primary objective of the study will be to assess safety via minor and major adverse events. Secondary objective will be improvement of OA symptoms as assessed by the WOMAC and VAS scores at each follow-up visit. Subjects will continue to be followed according to the institutional standard of care after they complete the 12-month study visit.

# 5. Treatments and Assessments

Subjects will be treated with a genicular artery embolization (GAE) procedure performed with Embozene Microspheres. The microspheres will be delivered in a saline-contrast medium solution and will be delivered to the arteries supplying the areas of the subject's pain. A complete description of the technical protocol to be followed is provided in Appendix C.

After GAE, follow-up visits will take place at 1 week ( $\pm$  4 days), 1 month ( $\pm$  2 weeks), 3 months ( $\pm$  2 weeks), 6 months ( $\pm$  2 weeks), and 12 months ( $\pm$  2 weeks) from the date of treatment. Subjects who cannot present in person to the clinic at the 3, 6 or 12 month visit due to travel restrictions from the COVID-19 virus will conduct the follow-up visit over the phone. A schedule of study events and study flow chart are presented in Appendices A and B, respectively.

# 5.1 Visit 1: Screening/Baseline (within 8 weeks of GAE)

Subjects that meet all eligibility criteria listed in Section 3 above are eligible for participation in this study.

Prior to enrollment, each patient will have the following assessments performed:

- Obtain written informed consent
- Medical history, including demographics
- Physical examination including vital signs
- Western Ontario and McMaster Universities Osteoarthritis Index (WOMAC, version 3.1) questionnaire
- Visual analog scale (VAS) score
- Laboratory evaluation: serum complete blood count and basic metabolic panel
- Knee MRI without contrast. If patients cannot undergo MRI (e.g. pacemaker, significant claustrophobia), then CT of the knee without contrast will be performed. If a knee MRI or CT has already been performed within 6 months of Visit 1, that will be accepted.
- Knee x-ray (within 6 months of Visit 1)
- Evaluation for moderate sedation

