#### 5.2 Visit 2: Genicular Artery Embolization

The following data will be collected during each GAE procedure:

- Technical success of GAE, defined as successful catheterization and embolization
- Procedure time, duration of hospitalization, duration of catheterization, fluoroscopy dose, volume of embolic delivered, arteries embolized.

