#### 5.3 Visits 3-7: Post GAE Follow-Up

Subjects will have the following assessments performed:

- Physical examination including vital signs
- WOMAC and VAS questionnaires (at visits 4-7)
- Review of adverse events
- Knee MRI (at visit 5: 3 month follow-up). If patients cannot undergo MRI (e.g. pacemaker, significant claustrophobia), then CT of the knee without contrast will be performed.
- Knee x-ray (at visit 7: 12 month follow-up)

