# **Appendix A: Schedule of Study Events**

	Visit 1	Visit 2	Visit 3	Visit 4	Visit 5	Visit 6	Visit 7	
	Screening (within 8 weeks of Day 1)	Treatment (Day 1)	Week 1 (day 4-10)	Month 1 (4 weeks ± 2 weeks)	Month 3 (12 weeks ± 2 weeks)	Month 6 (24 weeks ±2 weeks)	Month 12 (52 weeks ± 2 weeks)	
Informed Consent	Х							
Eligibility criteria assessment	X							
Demographics	X							
Medical History	Х							
Concurrent Medical Conditions	Х							
Physical Examination	X		Х	Х	Х	Х	Х	
Vital Signs	Х		Х	Х	Х	Х	Х	
Laboratory Evaluations 	Х							
WOMAC	X			Х	Х	Х	Х	
VAS	Х			Х	Х	Х	Х	
PRO and PGIC							Х	
Knee x-ray 	Х						Х	
Knee MRI 	X				Х			
GAE		Х						
Adverse Events		Х	Х	Х	Х	Х	Х	
Concomitant Medications	X	X		X	X	X	X	
Protocol violations	X	Х	Х	Х	Х	Х	Х	

 Laboratory evaluations include complete blood count and serum chemistry

 Screening knee X-Ray can be performed within 6 months before Visit 1.

 Screening knee MRI can be performed within 6 months before Visit 1. If patients cannot undergo MRI (e.g. pacemaker, significant claustrophobia), then CT of the knee without contrast will be performed.

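### The only pre-treatment WOMAC and VAS come from the screening visit whose VAS appears to decide entry, so regression to the mean adds to the change from baseline: directly for VAS, indirectly for WOMAC

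*Combined protocol and SAP*

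**What the plan says.** - **Baseline.** Protocol Section 5.1 is headed "Visit 1: Screening/Baseline (within 8 weeks of GAE" and lists WOMAC and VAS among its assessments. The column in Appendix A reads "Screening (within 8 weeks of Day 1".
- **No second pre-treatment score.** Section 5.2 introduces the treatment-day data with "The following data will be collected during each GAE procedure" and lists technical and procedural items only. Section 5.3 places the later scores as "WOMAC and VAS questionnaires (at visits 4-7". Appendix A agrees: WOMAC and VAS are marked at Visits 1, 4, 5, 6 and 7, and eligibility assessment at Visit 1 only. Section 4 also implies scores at week 1, which Section 5.3 and Appendix A do not, but that would not add a pre-treatment score.
- **Entry on VAS.** Section 3.1 requires "Moderate-severe knee pain as determined by visual analog scale" of at least 4. Section 3.2 excludes "Mild knee pain as determined by visual analog scale < 4".
- **No comparator.** Section 4 describes a "single-center, prospective, single arm investigational study" of 40 patients.
- **Use of baseline.** Section 2.2 assesses efficacy outcomes "compared to baseline values when appropriate". Section 9 tests the mean WOMAC change from before treatment to 12 months against zero, two-sided at 0.05, and applies the same methods to the other timepoints.

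No run-in, repeat baseline or allowance for regression to the mean is described.

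**The concern.** A single pain score is partly lasting level and partly the state of that day. Admitting only patients who score at or above a cut-off favours those whose reading was high that day. The day's excess is not carried forward, so the next mean is lower even if nothing was done. A control arm would show the same fall and cancel it; this study has none.

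The error has one direction: it makes GAE look better. Adjusting for baseline WOMAC, as the Section 9 model does, does not remove it, because with one arm the adjusted mean change at the average baseline is still the observed mean change. Every comparison from baseline, and the time-to-improvement curve, starts from the same value. At stake is how far the efficacy estimate, a secondary objective, can be read as the effect of the procedure.

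**Working it through.** The plan states no SD, test-retest correlation or regression allowance for WOMAC or VAS, so there is no figure of its own to reproduce.

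**Inputs from the documents:** cut-off VAS 4 (Sections 3.1, 3.2); n = 40 and one arm (Section 4); two-sided 0.05 test of zero change (Section 9); WOMAC total 20 + 8 + 68 = 96 points (Section 8.1). The cut-off of 4 is read as lying on a 0-10 scale.

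**Assumptions:** screened VAS roughly normal, mean 5 to 7, SD 2; reliability ρ 0.6 to 0.8; WOMAC SD 15 to 18; VAS-WOMAC correlation 0.6 to 0.7 on the same day, and 0.3 to 0.48 between the Visit 1 VAS and the 12-month WOMAC.

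**Step 1, strength of selection.** With z = (4 − mean)/SD, λ = φ(z)/(1 − Φ(z)):
- mean 5: z = −0.5, λ = 0.352/0.691 = 0.509
- mean 6: z = −1.0, λ = 0.242/0.841 = 0.288
- mean 7: z = −1.5, λ = 0.130/0.933 = 0.139

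**Step 2, VAS.** Spurious fall = (1 − ρ) × SD × λ:

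| Screened mean | ρ = 0.8 | ρ = 0.6 |
|---|---|---|
| 5 | 0.2 × 2 × 0.509 = 0.20 | 0.4 × 2 × 0.509 = 0.41 |
| 6 | 0.2 × 2 × 0.288 = 0.12 | 0.4 × 2 × 0.288 = 0.23 |
| 7 | 0.2 × 2 × 0.139 = 0.06 | 0.4 × 2 × 0.139 = 0.11 |

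**Step 3, WOMAC.** Selection acts only through VAS. Spurious fall = (same-day correlation − 12-month correlation) × WOMAC SD × λ:
- mean 5, low end: (0.60 − 0.48) × 16.5 × 0.509 = 1.0 point
- mean 5, high end: (0.70 − 0.35) × 18 × 0.509 = 3.2 points; with VAS SD 2.5 (λ = 0.562), 3.5 points
- mean 7, the same two correlation pairs at VAS SD 2: 0.12 × 16.5 × 0.139 = 0.3 and 0.35 × 18 × 0.139 = 0.9 points

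**Step 4, false-positive rate with no effect.** A paired t-test stands in for the Section 9 model.
- *VAS, by simulation* (n = 40, thousands of trials per setting): about 18% to 31% at mean 5, 9% to 13% at mean 6 and 6% to 7% at mean 7. At means 5 and 6 nearly all rejections are apparent improvements. Repeat runs moved these by about one percentage point.
- *WOMAC, by simulation* (SD 16.5): about 8% to 19% at mean 5, 6% to 10% at mean 6 and 5% to 7% at mean 7.
- *Sensitivity of the WOMAC rate.* It also depends on WOMAC's own correlation between baseline and 12 months, which the documents do not give. At 0.7, the standard error of mean change is 16.5 × √(2 × 0.3)/√40 = 2.02. A fall of 1.0 point gives 1.0/2.02 = 0.5 standard errors and a rate near 8%. A fall of 0.35 × 16.5 × 0.509 = 2.9 points gives 1.45 standard errors and about 30%. So WOMAC is below VAS under most assumed correlations, but not all.

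**Step 5, with a second baseline.** If Visit 1 error is independent of later error, the expected fall is zero and the VAS rate returns to about 5%. If correlation decays with time (0.7 from Visit 1 to Visit 2, 0.6 from Visit 1 to 12 months; mean 5), the residual is (0.7 − 0.6) × 2 × 0.509 = 0.10 point, against 0.41 under the current plan.

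**The case against.** **No VAS test is specified.** Section 9 specifies a test for WOMAC only, and WOMAC has no cut-off. A reader might infer that the planned efficacy test carries a 31% false-positive rate. The documents do not support that: the figure belongs to a VAS test the plan does not define. This stands.

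**The large rates need a screened mean near 5.** Nothing in the documents supports that value. The only VAS level given is the earlier embolization study's baseline of 72 on a 0-100 scale (Section 1, Rationale), and near 7 both rates are close to nominal. This stands as a limit on size. It does not settle the matter, because that is the mean of treated patients in another population, and entry here reaches down to 4.

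**The bias is small beside the hoped-for effect.** The earlier study fell from 72 to 13 at 12 months, or 5.9 points on 0-10. A spurious 0.06 to 0.41 is 1% to 7% of that. A reader might infer that most of any improvement would be regression; these figures do not support it. The false-positive rate matters chiefly if the true effect is near zero.

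**The entry score is not named.** No sentence says that the Visit 1 VAS is the qualifying one. It is, however, the only VAS scheduled before treatment, and eligibility is assessed at that visit alone. Entry also requires local tenderness and at least three months of failed conservative treatment; this does not undo selection on VAS.

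**A repeat leaves the larger single-arm problems.** Placebo response and natural history remain, and a score on the procedure day may reflect anticipation. Both stand, and limit what the fix can claim.

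**Conclusion.** The point holds as a modest, one-directional bias in a secondary objective. It is direct for VAS (about 0.06 to 0.41 points on 0-10) and indirect for WOMAC (about 1 to 3.5 of 96 points at screened mean 5, under 1 point near mean 7). Its effect on a test of no change ranges from negligible to material, depending on how many screened patients lie near the cut-off. All sizes rest on assumed means, SDs and correlations; that the Visit 1 VAS decides entry is a strong inference, not a stated rule.

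A reader might go further and conclude that the efficacy result would be invalid, or that the study's main conclusion is at risk. Neither follows: the primary objective is safety, which this does not touch. It is a cheap improvement, not a fatal flaw.

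**What to change.** - Repeat WOMAC and VAS at Visit 2, before sedation and embolization. Add both to Section 5.2 and mark them in the Visit 2 column of Appendix A.
- State in Section 9 that the Visit 2 values are the baseline for all change analyses, including time to improvement. Keep the Visit 1 VAS for eligibility only, so that the new baseline is not itself selected on.
- Report change from Visit 1 as a sensitivity analysis.
- State in Section 9 that the change from baseline still contains placebo response, natural history and possibly some residual regression (about 0.1 VAS point in the example above).

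**Cost.** Section 8.1 puts the WOMAC at about 12 minutes; the VAS adds little, and the visit is already scheduled. The estimated change may be somewhat smaller, and procedure-day anticipation may affect the scores. The change helps only patients not yet treated, because a missing pre-procedure score cannot be recovered later.
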